	
product/placebo co-administered with the standard symptomatic therapy:
 
Group A – the IMP was XC221 at a daily dose of 100 mg, co-administered with the standard symptomatic therapy;
 
Group B – the IMP was XC221 at a daily dose of 200 mg, co-administered with the standard symptomatic therapy;
 
Group C – placebo, co-administered with the standard symptomatic therapy.
 
During the trial, the randomized patients received the study therapy on an in- or outpatient basis during 3 days under control of an investigator at the following visits: Visit 1 (Day 1), Visit 2 (Day 2), and Visit 3 (Day 3).
 
After the 3-day treatment period, the patients were followed up for the subsequent 11 ± 1 days (the follow-up period).
 
During the follow-up period, the following visits were performed: Visit 4 (Day 4), Visit 6 (Day 6), and Visit 9 (Day 14 ± 1) – the patient visited the study center in person; Visit 5 (Day 5), Visit 7 (Day 7), and Visit 8 (Day 8) could be made either in person or on an in-patient/outpatient basis or as morning and evening telephone calls to assess patient's wellbeing. Visit 9 (Day 14 ± 1) was made 14 ± 1 days after treatment initiation. After completing Visit 9 (Day 14 ± 1), patients' participation in the clinical trial was considered completed.
 
At Visit 1 (Day 1), diaries were handed over to the patients so that they could write down the body temperature values. During the treatment period, the patient was supposed to measure his/her body temperature twice a day: in the morning (at 8–11 a.m.) and in the evening (8–11 p.m.). The temperature measurements results were written down in the patient's temperature diary.
 
During the trial, starting with Visit 0 (screening visit) through Visit 8 (Day 8), the investigator evaluated the severity of the symptoms of influenza/acute viral URI daily (in the morning and in the evening) using the modified Jackson scale, either in person or in a telephone conversation. At Visits 1 (Day 1) through 4 (Day 4), the first measurement of body temperature and evaluation of symptom severity were carried out

--	---

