	
At Visit 1 (before the first dose of IMP/placebo was taken), Visit 4, and Visit 6, patients' blood samples were collected to analyze serum concentrations of MxA protein, C-reactive protein, and cytokines 6Ckine, BCA-1, CTACK, ENA-78, Eotaxin, Eotaxin-2, Eotaxin-3, Fractalkine, GCP-2, GM-CSF, Gro-α, Gro-β, I-309, IFN-γ, IL-1β, IL-2, IL-4, IL-6, IL-8, IL-10, IL-16, IP-10, I-TAC, MCP-1, MCP-2, MCP-3, MCP-4, MDC, MIF, MIG, MIP-1α, MIP-1δ, MIP-3α, MIP-3β, MPIF-1, SCYB16, SDF-1α+β, TARC, TECK, and TNF-α.

The number of patients screened/randomized, and patients who completed the study	
Screened patients: 121 Randomized patients: 120 Patients who completed the study: 120

Inclusion criteria:	
1. Men and women aged 18 to 45 years (inclusive).2. Clinically diagnosed mild or moderate influenza or acute viral URI.3. Patient's body temperature at screening $\geq 37.5^{\circ}\text{C}$ and at least one intoxication or catarrhal symptom from the ones listed in the modified Jackson scale, with severity grade estimated as score ≥ 2.4. Uncomplicated course of influenza or acute viral URI based on assessment of clinical symptoms.5. The interval between the onset of the earliest symptoms of the disease and enrollment (administration of the first dose of IMP/placebo) is no longer than 36 hrs.6. Women of reproductive age (who are not in menopause and who have not undergone surgical sterilization) and men who have sexual activity should use a reliable method of contraception (acceptable methods of contraception in this study are: intrauterine devices, oral contraceptives, contraceptive patch, long-acting injectable contraceptives, a double barrier method (condom with spermicide, diaphragm with spermicide)) throughout the study period and 30 days after the last dose administration of IMP/placebo.7. A patient agrees to adhere to the treatment regimen, visits and laboratory examinations provided by the protocol.

	8. Signed Informed Consent Form.

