	
18. Time to resolution (score 0) of each symptom in the modified Jackson scale (sneezing, rhinorrhea, nasal congestion, cough, fever, malaise, chills, headache, myalgia, sore throat, itchy throat, and hoarseness) since treatment initiation in the population of patients in whom the respective symptom was evaluated as score 2 or 3 at Visit 0 (Day 0);
 
19. Time to resolution (score 0) of each symptom in the modified Jackson scale (sneezing, rhinorrhea, nasal congestion, cough, fever, malaise, chills, headache, myalgia, sore throat, itchy throat, and hoarseness) since the onset of the earliest symptoms of the disease in the population of patients in whom the respective symptom was assessed as score 2 or 3 at Visit 0 (Day 0);
 
20. The percentage of patients having score 0 for each symptom in the modified Jackson scale (sneezing, rhinorrhea, nasal congestion, cough, fever, malaise, chills, headache, myalgia, sore throat, itchy throat, and hoarseness) on days 2, 3, 4, 5, 6, 7, and 8 after treatment initiation in the population of patients in whom the respective symptom was evaluated as score 2 or 3 at Visit 0 (Day 0);
 
21. The percentage of patients having score 0 for each symptom in the modified Jackson scale (sneezing, rhinorrhea, nasal congestion, cough, fever, malaise, chills, headache, myalgia, sore throat, itchy throat, and hoarseness) on days 2, 3, 4, 5, 6, 7, and 8 after the onset of the earliest symptoms in the population of patients in whom the respective symptom was evaluated as score 2 or 3 at Visit 0 (Day 0).

Safety endpoints:	
Secondary endpoint:
 
frequency of adverse events (AEs) and serious adverse events (SAEs) in the XC221 group and in the placebo group.
 
Tolerability was evaluated as good, fair, and poor based on the presence/absence of adverse drug reactions causing treatment suspension or discontinuation.

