
It was expected that the optimal dose of the investigational medicinal product (XC221 100 mg or XC221 200 mg) would be selected in this trial by exploratory data analysis. The optimal IMP dose was supposed to be selected by the Sponsor according to the treatment group that would have the minimum median time to reach the effect for the primary endpoint but a similar or superior safety profile compared to that in the remaining groups. It was assumed that if the median time to reach the effect for the primary endpoint in two dose groups was equal, the smaller dose would be selected.

The sample size was calculated using the PASS 14 software according to the data obtained in the previous trial of the same Sponsor (FLU-XC8-01). In it, the hazard rates for a similar endpoint were found to be 0.83 and 1.23 for the placebo and treatment groups, respectively. The sample size for the present trial was estimated so that the width of 95% two-sided confidence interval of hazard rate was no greater than the twofold difference in hazard rates between the treatment and placebo groups in a similar study (0.8); the percentage of censored observations was $\leq 5\%$. Hence, it was found that the sample size required per group was 39 subjects. The selected significance level $\alpha = 0.05$; the pre-set power was 80%. Having assumed that the percentage of patients withdrawn throughout the study was 2.5%, 40 patients needed to be screened for each group. Size of the placebo group was equal to that of the treatment groups. Hence, a total of 120 patients were planned to be randomly assigned into three groups at a 1:1:1 allocation ratio (40 subjects into each group: the placebo group and the groups treated with XC221 100 mg or XC221 200 mg). Assuming

that the probability of subject withdrawal at screening was ~15%, up to 140 patients were to be screened.

This was a multicenter trial, with patients recruited on a competitive basis. In order to minimize the bias, each study center could randomize no more than 30% (36 patients) of the total sample size.

Statistical methodology

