All variables for analysis were presented using the descriptive statistical methods. An analysis was conducted to compare groups at primary and secondary endpoints. Categorical variables were analyzed using the χ^2 test; the two-tailed Fisher's exact test was used if more than 20% of expected frequencies were < 5. The areas under "variable versus time" curves were calculated using the trapezoidal rule. Groups were compared in terms of quantitative variables using ANOVA/ANCOVA; the non-parametric alternative was employed if the assumptions underlying the method were not met. Survival analysis (plotting the Kaplan–Meier curves, comparing the hazard functions using the Gehan–Wilcoxon test) and the stratified Cox regression model were used for the censored Time-to-Event data. The secondary endpoint data for patients prematurely withdrawn from the study were substituted using the LOCF algorithm.

Interim analysis

Interim analysis was not involved in this study.

Analysis groups

Three equal-sized groups, with 40 subjects per group (2 groups receiving different doses of IMP and the placebo group) were planned for this study. The groups treated with IMP were supposed to be compared in a pairwise manner to the placebo group; it was also planned that the treatment groups would be compared to each other.

Baseline comparability

The baseline data (demographic and anthropometric characteristics, as well as disease duration documented prior to treatment initiation) were compared between the groups in the Full Analysis Set population. If significant differences between treatment groups were revealed for any baseline parameter, sensitivity analysis was performed to test

whether the conclusions about the efficacy remained unchanged after applying a correction for different baseline parameters in groups.

Safety analysis

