The safety population consisted of all the patients treated with any dose of IMP/placebo. Safety parameters (vital signs, laboratory data, and AEs) were descriptively analyzed for each group. The numbers of AEs and patients with AEs were summarized according to their treatment group and categorized according to the system organ classes and preferred terms. Additional summarizing was performed for severity of AEs and their relationship to IMP. SAE narratives were additionally made in a separate analysis. Patients withdrawn prematurely from the trial can be found in the list of patients and were categorized according to the main reason for withdrawal (in each treatment group).

Tolerability analysis

Frequency tables were plotted to analyze the tolerability data (in the safety population); a conclusion regarding the potential differences in tolerability between the analyzed samples was drawn according to these tables.

Efficacy analysis

The main efficacy analysis for the primary endpoint was carried out using the Full Analysis Set population. Sensitivity analysis in the population of patients with verified viral infection and the Per Protocol population was conducted. Sensitivity analysis using the stratified Cox model was carried out separately for the Per Protocol population, with the following covariates: "study center", "presence of viral infection", and "concomitant treatment with NSAIDs".

Secondary endpoint analysis was conducted in the Full Analysis Set population and the population of patients with verified viral infection. Concentrations of C-reactive protein and 6Ckine, BCA-1, CTACK, ENA-78, Eotaxin, Eotaxin-2, Eotaxin-3, Fractalkine, GCP-2, GM-CSF, Gro- α , Gro- β , I-309, IFN- γ , IL-1 β , IL-2, IL-4, IL-6, IL-8, IL-10, IL-16, IP-10, I-TAC, MCP-1, MCP-2, MCP-3, MCP-4, MDC, MIF, MIG, MIP-1 α , MIP-1 δ , MIP-3 α , MIP-3 β , MPIF-1, SCYB16, SDF-1 $\alpha+\beta$, TARC, TECK, and TNF- α cytokines were analyzed in the Full Analysis Set population.

	
Software
 
Specialized SAS software (version 9.4) was used for statistical analysis.

--	---

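### Adjustment for baseline imbalance waits for a significant baseline test; baseline Jackson score and temperature are not on the list tested, and neither severity nor time since onset is a named Cox covariate

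*Combined protocol and SAP*

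**What the plan says.** - **Baseline comparability.** The variables compared are "demographic and anthropometric characteristics, as well as disease duration documented prior to treatment initiation". The rule is then "If significant differences between treatment groups were revealed for any baseline parameter, sensitivity analysis was performed to test" whether the efficacy conclusions hold after a correction. No model is given for that correction.
- **Statistical methodology.** "Groups were compared in terms of quantitative variables using ANOVA/ANCOVA", with a non-parametric fallback. No covariate is named. The stratified Cox model is mentioned for time-to-event data in general, without a population or covariates.
- **Efficacy analysis.** The main primary-endpoint analysis is in the Full Analysis Set. "Sensitivity analysis using the stratified Cox model was carried out separately for the Per Protocol population, with the following covariates": study centre, presence of viral infection and concomitant NSAIDs.
- **Hypothesis testing.** The primary test is Gehan-Wilcoxon, with no covariate stated.
- **Data available.** In Methodology, "starting with Visit 0 (screening visit) through Visit 8 (Day 8), the investigator evaluated the severity of the symptoms" twice a day. Screening temperature is needed for eligibility. A pre-dose value of each therefore exists.
- **Secondary endpoints 18-21.** These are analysed "in the population of patients in whom the respective symptom was evaluated as score 2 or 3 at Visit 0 (Day 0"), so they condition on the starting score of the symptom concerned. Several other secondary endpoints are timed from symptom onset.

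**The concern.** The primary endpoint is reached when every item of the modified Jackson scale has fallen to 1 or below. Besides fever, entry requires only "at least one intoxication or catarrhal symptom from the ones listed in the modified Jackson scale, with severity grade estimated as score" of 2 or more, and the scale has 12 items. One patient may need a single item to improve and another may need many. Starting severity is therefore a plausible predictor of the outcome, yet it is not on the baseline list and is not a named covariate in any analysis.

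The trigger is a second weakness. Whether to adjust depends on how prognostic a variable is, not on the p-value of a baseline comparison. A chance imbalance in a strong prognostic factor can be too small to reach significance and still move the estimated effect.

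Two things are at stake. In a given randomisation, an imbalance in starting severity stays in the estimate, including the medians behind the dose rule, which picks "the treatment group that would have the minimum median time to reach the effect for the primary endpoint", subject to safety. Precision is also lost in the Jackson area under the curve (AUC), the daily Jackson means and any Cox estimate.

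**Working it through.** **1. The plan's sample size.** The concern disputes no printed number, but the check uses the plan's arm size. From Sample size justification: hazard rates 0.83 and 1.23, 95% CI width at most 0.8, 5% censored, 2.5% withdrawn. At rate 1.23 with 37 events, the width is 2 × 1.96 × 1.23/√37 = 0.793. Then 37/0.95 gives 39, and 39/0.975 gives 40 per arm. The plan's figures reproduce. Expected events per pairwise comparison: 80 × 0.95 = 76.

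**2. What a baseline test can flag.** The standard error of a standardised difference is √(2/40) = 0.2236.
- Pairwise t test: 1.991 × 0.2236 = 0.445 SD is needed for p < 0.05.
- Three-group F test (critical value 3.074 on 2 and 117 df): the largest pairwise gap must reach √(3 × 3.074/40) = 0.480 SD if one arm stands apart, or √(4 × 3.074/40) = 0.554 SD if the third arm lies midway.

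**3. How often chance produces a relevant gap.**
- At least 0.3 SD in either direction: 2(1 − Φ(0.3/0.2236)) = 18.0% per pair.
- At least 0.4 SD: 7.4% per pair.
- At least one of the two dose-placebo pairs: 30.3% and 13.1% (1,000,000 draws).
- Gaps between 0.30 SD and the significance threshold, too small to trigger a correction, make up about 13% of pairwise comparisons.

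**4. Conditional bias with no true effect.** The documents do not say how prognostic severity is, so the strength h (hazard ratio per SD) is assumed. Simulation of 40 vs 40: hazard = 0.83 × exp(β × treatment − ln(h) × S), with S standard normal, 5% random censoring, β = 0, treated arm forced to start milder, 12,000 runs per setting.

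| Gap | h | Mean HR, unadjusted | Mean HR, adjusted | Gehan-Wilcoxon rejects |
|---|---|---|---|---|
| 0.3 SD | 1.25 | 1.07 | 1.00 | 5.9% |
| 0.3 SD | 1.5 | 1.11 | 1.00 | 5.9% |
| 0.3 SD | 2.0 | 1.17 | 1.00 | 6.5% |
| 0.4 SD | 1.25 | 1.09 | 1.00 | 6.4% |
| 0.4 SD | 1.5 | 1.16 | 1.00 | 7.7% |
| 0.4 SD | 2.0 | 1.24 | 1.00 | 10.8% |

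With no forced gap, Gehan-Wilcoxon rejects in 4.6-5.3% of runs (5,000 per setting), so the average type I error is intact.

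**5. Power.** Same model with β = ln(1.23/0.83), a conditional HR of 1.48, 12,000 runs per setting.

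| h | Gehan-Wilcoxon | Cox unadjusted | Cox adjusted | Cox gain (points) |
|---|---|---|---|---|
| 1.0 | 31.5% | 39.4% | 39.5% | 0 |
| 1.25 | 30.2% | 36.9% | 39.5% | 3 |
| 1.5 | 27.9% | 32.0% | 38.9% | 7 |
| 2.0 | 23.7% | 25.2% | 38.9% | 14 |

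If severity is not prognostic, adjustment costs essentially nothing.

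**6. ANCOVA.** For an assumed baseline-outcome correlation r, residual variance is multiplied by 1 − r², equivalent to 1/(1 − r²) − 1 more patients. The power column assumes a 0.5 SD effect (noncentral t). The last column is the shift that a 0.4 SD baseline gap leaves in an unadjusted AUC, r × 0.4.

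| r | Variance factor | Equivalent extra patients | Power, unadjusted to adjusted | Unadjusted shift |
|---|---|---|---|---|
| 0.3 | 0.91 | 10% | 60% to 64% | 0.12 SD |
| 0.5 | 0.75 | 33% | 60% to 72% | 0.20 SD |
| 0.7 | 0.51 | 96% | 60% to 87% | 0.28 SD |

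**The case against.** - **The plan may be silent rather than wrong.** The general sentence on Cox regression limits neither population nor covariates, and ANCOVA allows a baseline covariate. This stands as a reading: severity adjustment is unspecified, not excluded. But an unspecified covariate is not a planned adjustment.
- **The trigger refers to any baseline parameter, which could reach beyond the bracketed list.** Day 1 Jackson and temperature means are also compared as secondary endpoints, so a large early difference would probably be seen. This is partial cover, because those means are not strictly pre-dose. On the wider reading the significance trigger still applies.
- **Time since onset is better covered than severity.** Disease duration is on the baseline list, entry is capped at 36 hours, and many secondary endpoints are timed from onset. This stands. The simulations model severity only, so no size is given for time since onset.
- **The harm needs an unlucky draw and a strong covariate.** A gap in the treated arm's favour has half the two-sided frequency: 9.0% for 0.3 SD and 3.7% for 0.4 SD. The 10.8% rejection rate needs h = 2.0 as well. This is fair, although a gap the other way would hide a real effect.
- **The unadjusted power levels depend on taking 1.48 as the conditional ratio.** The plan's rates are stated without covariates. If 1.48 is the unadjusted ratio, unadjusted power would not fall in this way. Adjustment would still gain power, but the levels are not anchored.
- **Little changes for the main decision.** The primary test and the dose rule are untouched, and the plan calls dose selection exploratory. This stands for the primary endpoint, where the remedy is a supportive check. For the AUC and daily means it improves a planned analysis.

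**Conclusion.** The concern holds. The printed baseline list omits the Jackson score and temperature. Correction depends on a significance test that cannot see pairwise gaps below about 0.445 SD. The one model with named covariates is Per Protocol and includes neither severity nor time since onset. Endpoints 18-21 condition on severity; the primary endpoint, the AUC and the daily Jackson means do not.

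The size rests wholly on assumed prognostic strength. At 1.25 per SD the effect is small. At 1.5 to 2.0 per SD, a 0.4 SD chance gap produces a spurious mean hazard ratio of 1.16 to 1.24, which is material beside the planning ratio of 1.23/0.83 = 1.48. This is a change that should be made, not a flaw that invalidates the trial. Confidence is high in the textual omission and lower in its practical consequence.

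**What to change.** Drop the significance trigger and adjust whatever balance is observed.

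1. Add a supportive Cox model for the primary endpoint in the Full Analysis Set. Its covariates are baseline total Jackson score (the last score before the first dose, otherwise Visit 0) and hours from symptom onset to first dose.
2. Name the ANCOVA covariate: baseline Jackson score for the AUC and daily Jackson means, and baseline temperature for daily mean temperature.
3. Add baseline Jackson score and temperature to the baseline table, reported descriptively without tests.
4. Keep Gehan-Wilcoxon as the primary test and the dose rule as written. Report the adjusted hazard ratio beside the test result and beside the medians used for dose selection.

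The cost is SAP wording and two model parameters against about 76 events per pairwise comparison. The data are already collected. The document reports that all 120 randomised patients completed, so analyses added after the data were seen must be labelled post hoc. They can be pre-specified in the next trial.

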Aim and objectives of the study:	
Study aim:
 
The aim of this clinical trial was to evaluate safety, tolerability, and efficacy, as well as to determine the optimal dose of XC221 co-administered with the standard symptomatic therapy to treat influenza and acute viral URI.
 
Study objectives:
 
1. To evaluate the safety of XC221 100 mg and 200 mg vs placebo, co-administered with the standard symptomatic therapy to treat influenza and acute viral URI by frequency of adverse events (AEs).2. To evaluate the efficacy of XC221 100 mg and 200 mg vs placebo, co-administered with the standard symptomatic therapy to treat influenza and acute viral URI by its effect on main manifestations of the disease (symptom intensity and duration) using the modified Jackson scale.3. To determine the optimal dose of XC221 among the suggested doses (100 and 200 mg per day) by analyzing efficacy, safety, and tolerability of IMP.4. To evaluate the dynamics of MxA protein blood concentration during the administration of XC221 100 mg and 200 mg vs placebo.5. To evaluate the dynamics of C-reactive protein (CRP) blood concentration during the administration of XC221 100 mg and 200 mg vs placebo.6. To evaluate the dynamics of blood concentrations of 6Ckine, BCA-1, CTACK, ENA-78, Eotaxin, Eotaxin-2, Eotaxin-3, Fractalkine, GCP-2, GM-CSF, Gro-α, Gro-β, I-309, IFN-γ, IL-1β, IL-2, IL-4, IL-6, IL-8, IL-10, IL-16, IP-10, I-TAC, MCP-1, MCP-2,

	
MCP-3, MCP-4, MDC, MIF, MIG, MIP-1α, MIP-1δ, MIP-3α, MIP-3β, MPIF-1, SCYB16, SDF-1$\alpha+\beta$, TARC, TECK, and TNF-α cytokines during the administration of XC221 100 mg and 200 mg vs placebo.

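### The safety objective and the dose-selection rule compare arms on safety, but no stated analysis shows how large an adverse-event difference the data leave open

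*Combined protocol and SAP*

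**What the plan says.** - **Aim and objectives, objective 1:** "To evaluate the safety of XC221 100 mg and 200 mg vs placebo, co-administered with the standard symptomatic therapy". The measure is AE frequency.
- **Sample size justification:** the dose "would be selected in this trial by exploratory data analysis". The sponsor takes the group with the shortest median time to the primary effect, provided it also has "a similar or superior safety profile compared to that in the remaining groups". The section does not say what counts as similar, on which safety parameter, or within what margin.
- **Safety analysis:** "Safety parameters (vital signs, laboratory data, and AEs) were descriptively analyzed for each group". AEs are tabulated by arm, by system organ class and preferred term, and by severity and relationship. The section names no between-arm difference, interval or test.
- **Tolerability analysis:** any conclusion about differences between the samples is read from frequency tables.
- **Safety endpoints:** the item headed as a secondary endpoint is "frequency of adverse events (AEs) and serious adverse events (SAEs) in the XC221 group and in the placebo group".
- **Statistical methodology:** "An analysis was conducted to compare groups at primary and secondary endpoints". Categorical variables get a chi-square test, and the two-tailed Fisher "exact test was used if more than 20% of expected frequencies were < 5". Analysis groups adds that each dose is compared with placebo and the doses with each other.

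**The concern.** Both the objective and the safety condition for choosing a dose ask a comparative question. The analyses on offer are either a description of each arm or, if the general rule on secondary endpoints reaches AEs, a p-value. Neither says how large an AE excess is still compatible with the data.

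The sponsor would therefore apply 'similar or superior' either to raw counts or to a test that is unlikely to reject. A dose with a real excess could be passed as similar, and an equally safe dose could look worse by chance. A reader of the results could not tell how much excess remains possible. The point concerns the safety condition only, not the median-time condition.

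**Working it through.** **1. What the sample size was built for.** Inputs from Sample size justification: hazard rates 0.83 and 1.23, 95% interval width at most 0.8, up to 5% censored, 2.5% withdrawn.
- Target width: 2 × (1.23 − 0.83) = 0.80.
- Width for one exponential rate: 2 × 1.96 × rate / √events. With rate 1.23, events = (2 × 1.96 × 1.23 / 0.8)² = 36.3.
- Allowing for censoring: 36.3 / 0.95 = 38.2, rounded up to 39. Allowing for withdrawal: 39 / 0.975 = 40.

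The stated 39 and 40 reproduce. They rest on the efficacy hazard rate alone; safety played no part.

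**2. Which analysis of AEs is planned.** Safety analysis says description by group. Safety endpoints makes AE and SAE frequency a secondary endpoint, and Statistical methodology says secondary endpoints are compared, with a test for categorical data. On the other side, the sentence assigning secondary endpoints to the Full Analysis Set and the verified-infection population sits under Efficacy analysis, whereas AEs belong to the safety population. The text supports either reading.

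**3. What 40 per arm leaves open.** The documents give no AE rate and no margin, so rates of 5–30% and margins of 10–20 points are assumptions. For equal observed proportions p, the Newcombe half-width is √[(p − l)² + (u − p)²], where l and u are the Wilson limits. At 8/40, l = 0.105 and u = 0.348, giving √(0.095² + 0.148²) = 0.176. For non-inferiority with equal true rates, one-sided 0.025 and 80% power, n per arm = (1.96 + 0.84)² × 2p(1 − p) / margin².

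| AE rate, both arms | 95% CI for difference, 40 vs 40 | n per arm, 10-point margin | 15-point | 20-point |
|---|---|---|---|---|
| 5% | ±12.1 points | 75 | 34 | 19 |
| 10% | ±14.4 | 142 | 63 | 36 |
| 20% | ±17.6 | 252 | 112 | 63 |
| 30% | ±19.5 | 330 | 147 | 83 |

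Forty per arm is enough for a 15-point margin at about 5%, or a 20-point margin up to about 10%. It is not enough for a 10-point margin at any of these rates. For an event seen in 0 of 40, the two-sided 95% upper limit is 1 − 0.025^(1/40) = 8.8%.

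**4. If counts are read by eye.** Take X1 (dose) and X0 (placebo) as independent Binomial(40, p) and sum the joint probabilities.
- Equal true rates, P(X1 − X0 ≥ 3): 10% at a rate of 5%, 17% at 10%, 24% at 20%. Three patients are 3/40 = 7.5 points.
- True excess, P(X1 − X0 ≤ 2): 59% for a rise from 5 to 10%, 32% for 10 to 20%, 35% for 20 to 30%.
- For 20 to 30%, the dose shows no more AE patients than placebo 18% of the time.

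**5. If AE frequency is tested.** Exact two-sided Fisher power at 40 vs 40 is 4% for 5 vs 10%, 16% for 10 vs 20%, 12% for 20 vs 30% and 41% for 20 vs 40%. Five patients with an event against none gives p = 0.055. A non-significant result is the likely outcome even when the excess is real.

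**The case against.** The strongest objection is that the plan does provide a comparison. AE frequency is a secondary endpoint, secondary endpoints are compared, and the pairwise contrasts are named. That stands far enough to rule out a stronger reading that a reader might take from the Safety analysis section alone, namely that AEs are described and never compared. The documents do not support it; what they show is a conflict between sections. But a test does not repair the gap, because a p-value at this size does not show similarity and no interval for a difference is specified.

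A second tempting reading is that 40 per arm can never show similarity. That is not supported either: the answer depends on an AE rate and a margin that the documents do not give, and some combinations of low rate and wide margin are met.

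Third, descriptive AE tables are ordinary in a trial of this size, dose selection is called exploratory, and no formal safety-equivalence claim is planned. All of that is fair, and nothing here asks for a powered safety test. Safety is nonetheless a condition of the selection rule, and intervals suit exploratory work because they show what has not been excluded.

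Finally, intervals this wide will rarely separate the doses, and they leave the judgement open unless 'similar' is defined in advance. That stands, and the definition therefore belongs in the change.

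**Conclusion.** The concern holds in this form: the safety objective and the dose-selection rule are comparative, 'similar' is undefined, and neither per-arm description nor a chi-square or Fisher test shows what AE excess remains possible. With equal observed rates of 5–30%, an excess of about 12 to 20 points is not excluded.

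The conflict between sections and the missing definition rest on the text alone. The sizes rest on assumed AE rates and margins, 40 evaluable patients per arm and independent binomial counts. This is an inexpensive improvement that should be made, not a flaw that invalidates the trial, and it implies nothing about which dose is preferable.

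**What to change.** 1. For the proportion of patients with any AE, any related AE and any SAE, report the risk difference with a 95% CI (Newcombe or exact) in the safety population, for 100 mg vs placebo, 200 mg vs placebo and 200 mg vs 100 mg.
2. Have the sponsor state, before unblinding, what AE excess it would still call similar, and apply the selection condition to the intervals. If the treatment codes are already open, label that threshold post hoc.
3. Quote the upper limit wherever similarity is claimed. If the interval includes an excess beyond the threshold, report that no difference was detected and that an excess of up to X points is not excluded.
4. Reconcile Safety endpoints, Statistical methodology and Safety analysis on whether AE frequency is tested or only described. Adding a significance test alone would not meet the need, because its power is low.

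Cost: one extra table from data already collected, and a less favourable safety statement because the width of the intervals will be visible.
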